5.5 Activity 5 – Qualitative interviews with patients about pain management

NOTE: Amendment #3 covering Activity 5/ qualitative interviews was approved by the IRB in April 2019.

Brief description of activity: The study team will interview up to 30 patients (including DFCI inpatients and outpatients) about their experiences with a cancer diagnosis and chronic pain management. Interviews will be one-on-one, semi-structured, and conducted using the developed interview guide (see Appendix G). All interviews will be audio-recorded, transcribed, and coded for common themes. All patients for this activity will fall into one of two eligibility cohorts:

Cohort A = patients visiting DFCI for a regular appointment with ongoing chronic cancer pain management issues

OR

Cohort B = patients visiting DFCI via the outpatient care clinic or patients recently admitted to the DFCI inpatient clinic at BWH for an active pain crisis.

Human Subjects Research Category (NHSR, exempt, expedited, full review): Full review

Informed Consent: Written consent will be obtained from all patient participants.

Methods that will be used to identify potential subjects: Under a HIPAA waiver, study staff will look in the electronic medical record, scheduling systems, and inpatient lists to identify potentially eligible patients who meet the eligibility criteria. Study staff may also query Epic, administrative/operations/billing databases, order entry databases, and/or cancer registry databases to identify potentially eligible participants. Study staff may also accept potential patient referrals from site clinicians. Purposive sampling based on data from the electronic medical record (e.g., demographics, cancer stage, number of recent hospitalizations, number of prescription drugs) will be used to ensure that perspectives of diverse patients are included.

Activity 5 Patient Inclusion Criteria:

- Patients diagnosed with a metastatic or locally advanced solid tumor malignancy
- English-speaking
- Age ≥ 21
- Patient visiting the DFCI outpatient clinic
- OR**
- Patient admitted to the DFCI inpatient hospital
- Has chronic pain as the result of cancer
- Patients prescribed both a short-acting and long-acting opioid

Activity 5 Patient Exclusion Criteria:

- Long-standing history of chronic pain unrelated to cancer (i.e. arthritis) for which they were taking opioid pain medications before their cancer diagnosis
- Recent surgical procedure (less than 4 weeks prior) resulting in pain
- Inability to participate in a 60-90 minute interview, e.g. due to cognitive or physical limitations

Number of subjects: Up to 30 patients will take part in one-on-one interviews, OR interviews will be stopped once thematic saturation has been achieved.

When, where, and how potential subjects will be recruited: Potentially eligible patients will be identified by 1) referrals from clinic staff, and 2) by screening the EMR for outpatient solid tumor disease center clinic schedules, and 3) by screening the palliative care consult service inpatient lists. Once the study team identifies a potentially eligible patient, the team will reach out to the treating clinician for permission to approach for an interview. Patients will sign informed consent according to IRB procedures. A \$25 incentive will be provided after study completion.

Materials that will be used to recruit subjects: NONE – if eligible, the study team will approach patients in-person to discuss.

Duration of subject's participation in the study: Patients will take part in a one-time, 1-hour interview with the study team. All interviews will be in-person or over the phone.

Duration anticipated to enroll all study subjects: We anticipate that the interviews will take 6 months to complete. Analysis will follow, thereafter.

Study design: Semi-structured, qualitative interview

Description of all research procedures being performed: After signing consent, all study patients will take part in a one-on-one interview with the study team. Prior to the interview, all patients will complete a one-time baseline survey (see Appendix I). The baseline survey involves demographic questions as well as validated pain measures. Patients can complete the survey via hard copy or online via REDCap. Once completing the baseline survey, patients will participate in the one-time interview. The interviewer will follow the developed interview guide (see appendix G). Interviews will take approximately one hour and can be conducted in-person or over the phone.

As the study team member asks the interviewee questions from the interview guide, s/he will audio-record their responses and take notes. The audiotape and paper onto which s/he records their responses will NOT contain an identifier of any kind (to elaborate, it will NOT contain the interviewee's name, MRN, SSN; only a study ID number). After conducting each interview, we will store the interview responses (paper and audiotape) in a locked drawer in our office (D-1011). Once the data has been entered into an electronic medium, the electronic files will be kept on a secure, password-protected server at Dana-Farber Cancer Institute. The audio-recordings will be transcribed verbatim, using a secure system. All audio-recordings and study materials will be kept for 5 years following study completion, at which time they will be destroyed.

Monitor subjects for safety or minimize risks: Not applicable.

What data will be collected and how: (see appendix H)

Basic demographic information (i.e. to explore gender or age stratification in qualitative results) will be collected from all participants via chart abstraction. Collected information will include:

- **Cancer:** Patient's date of diagnosis, diagnosis (cancer type), stage at diagnosis, status of active curative or palliative treatment, and history and date of surgery related to cancer
- **Pain:** Patient seen palliative care (yes/no), patient's last pain rating, type of pain, and location of pain.
- **Prescribed Pain Medicines:** Patient's prescribed short-acting opioid, long-acting opioid, and non-opioid pain medications, and length of time taking opioids.

Statistical Analysis: Because interviews produce qualitative results, statistical analyses will not be employed as part of this study. Qualitative thematic analysis will use a grounded theoretical approach in which two or more investigators will code transcripts and assign labels using an open coding approach. Investigators will name concepts and revise coding until consensus is reached. Analyses will be conducted using NVIVO analytic software, which the study PI will receive training in as part of this project.

ENDPOINT: The study team will use the qualitative results to help develop and modify a new pain mobile health app for cancer patients.

6.0 Study-Wide Number of Subjects*

Please find the summary of study-wide number of subjects below:

Activity	Maximum # of participants
Activity 1	20 Cohort A patients 20 Cohort B patients 20 Cohort C clinicians 20 Cohort D clinicians
Activity 2	N/A
Activity 3	12 Cohort A patients 12 Cohort B patients 10 Cohort C clinicians
Activity 4	20 patients, 20 Nurse Navigators and 20 physicians and mid-level providers
Activity 5	30 patients
Total accrual	169 participants 
• 114 patients• 55 clinicians

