Activity 1 Eligibility: Focus groups and interviews will include patients, oncologists, oncology nurses, advance practice nurses, palliative care practitioners, or pharmacists. All groups and interviews will be supported by a member of the study team (PI, Co-I, project manager and/or research assistant).

Cohort A & Cohort B (Patients) Inclusion Criteria:

- Age \geq 21 years
- Patient diagnosed with a metastatic or locally advanced solid tumor malignancy
- Current or previous outpatient use of opioids for cancer pain
- Own a smartphone

Cohort A & Cohort B (Patients) Exclusion Criteria:

- Cognitive impairment
- Inability to speak English
- History of substance abuse

Cohort C & Cohort D (Clinicians) Inclusion Criteria:

Clinicians caring for outpatients with cancer (medical oncologists, oncology nurses, advance practice providers, palliative care practitioners, etc.) working at DF/HCC

Cohort C & Cohort D (Clinicians) Exclusion Criteria:

- Unwilling to participate

Number of subjects: Up to 20 patients in Cohort A will take part in cognitive content testing interviews, and up to 20 patients in Cohort B will take part in wireframe testing. Up to 20 clinicians in Cohort C will take part in interviews or focus groups, and up to 20 clinicians in Cohort D will take part in wireframe testing.

When, where, and how potential subjects will be recruited: For Cohorts A and B (Patients), the clinical/study staff will approach patients in-person during a clinic visit to see if they are interested in participating in either the content testing or the wireframe testing. If a patient is interested in participating, the site will have the participant sign consent (Appendices JA or JB) and set up a time for an interview. For Cohorts C and D (Clinicians), the study PI or his/her designee will send emails/call/discuss in-person to all potential working group and/or interview participants. If interested, the clinicians will be given a study letter (see Appendix K) explaining the expected participation, they will be given a brief demographic survey and the interview/focus group will be scheduled.

Materials that will be used to recruit subjects: None.

Duration of subject's participation in the study: All interviews or focus groups will be in-person or via phone participation and will take approximately 30-60 minutes.

Duration anticipated to enroll all study subjects: We anticipate that it will take six months to enroll all participants.

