Cohort A: Patient Lab UAT	
 • Patients diagnosed with a metastatic or locally advanced solid tumor malignancy • Age ≥ 21 • Currently on short AND/OR long-acting opioids • Own a smartphone • Has chronic pain as the result of cancer or cancer treatment 	
 • Cognitive impairment • Inability to speak English • History of opioid use disorder
Cohort B: Patient Field UAT	
 • Patients diagnosed with a metastatic or locally advanced solid tumor malignancy • Age ≥ 21 • Currently on short- AND/OR long-acting opioids • Own a smartphone with a data plan, and have access to Wifi • Patient receiving longitudinal care at the DFCI gastrointestinal cancer center (GCC) • Has chronic pain as the result of cancer or cancer treatment 	
 • Cognitive impairment • Inability to speak English • History of opioid use disorder
Cohort C: Clinician Lab UAT	
 • Oncology physicians, mid-level providers, and nurses from across outpatient DFCI palliative care and solid tumor programs. 	
 • Unwilling to participate

Number of subjects: Up to 32 participants will take part in Activity 3, including up to 12 participants in Cohort A, up to 12 participants in Cohort B, and up to 10 participants in Cohort C.

When, where, and how potential subjects will be recruited:

Cohorts A & B: Potentially eligible patients will be identified by 1) referrals from clinic staff, or 2) by screening the EMR for outpatient solid tumor disease center or palliative care clinic schedules. Once the study team identifies a potentially eligible patient, the team will reach out to the treating clinician for permission to approach.

Once approved to approach, the clinical/study staff will approach patients in-person during a clinic visit to see if they are interested in participating. Alternatively, the study staff can send eligible patients an introduction to the study via mail/email and call them to offer participation (Appendices VA or VB).

Interested participants will then review the study letter with a research team member (Appendix VA or VB) and if interested provide verbal consent. Next, they will set up a time for the interview (Cohort A) or initial study visit (Cohort B).

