	
 • Takes at least 1 opioid medication on most days • Own a compatible smartphone 
 • iPhone, have updated or willing to update it to the past 3 iOS version releases: iOS 12, iOS13, iOS 14). • Android flagship devices with more than 5% market share, last 2 android version releases: Android 9 Pie and Android 10) 	
 • Currently has or has had recurrent bowel obstructions • The following special populations are excluded: adults unable to consent, prisoners, and pregnant women.
(Cohorts B and C): Clinician Eligibility	
 • Physicians and mid-level providers practicing in participating clinics and caring for a patient on the study • Nurse Navigators working within participating clinics 	
 • Unwilling to participate

Number of subjects:

Cohort A: Up to 20 patients (the number of participants will depend on usability issues at 4 weeks) will be enrolled in the single-arm pilot study.

Cohort B: Up to 20 nurse navigators involved in the opioid management of patients in Cohort A.

Cohort C: Up to 20 physicians and mid-level providers responsible for opioid management of patients in Cohort A.

When, where, and how potential subjects will be recruited:

Cohort A: Potentially eligible patients will be identified by 1) referrals from clinic staff, and 2) by screening participating physician and mid-level providers' clinic schedules. After getting the treating clinicians' permission, the patient will be approached for participation. Patient approaches can occur through the following mechanisms dependent upon COVID-19 related research regulations and clinic operations at the time.

- In person approach: A research assistant (RA) will approach the patient in clinic to explain the study and offer participation. Interested participants will then review the study letter with a research team member (Appendix AA) and if interested sign consent. Next, they will set up a time for onboarding to the application.

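### Section 6.0 states a total accrual of 169 with 55 clinicians, but its own rows add to 204 with 90 clinicians; Section 5.3 gives 32 for Activity 3 where its cohorts add to 34

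*Combined protocol and SAP*

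**What the plan says.** The table in Section 6.0 (Study-Wide Number of Subjects) lists a maximum for each activity and closes with a total accrual of "169 participants", made up of 114 patients and 55 clinicians. Its Activity 4 row reads "20 patients, 20 Nurse Navigators and 20 physicians and mid-level providers".

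The clinician numbers also appear in the sections for each activity:

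- Section 5.1 (Activity 1): "Up to 20 clinicians in Cohort C will take part in interviews or focus groups". The same maximum of 20 is given for the other clinician group, Cohort D, which tests wireframes.
- Section 5.3 (Activity 3): "Up to 32 participants will take part in Activity 3". The same sentence then sets the cohort maxima at 12 for A, 12 for B and 10 for C. Cohort C is the clinician cohort.
- Section 5.4 (Activity 4): for Cohort B, "Up to 20 nurse navigators involved in the opioid management of patients in Cohort A"; the entry for Cohort C is "Up to 20 physicians and mid-level providers responsible for opioid management of patients in Cohort A".

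Section 25.0 (Local Number of Subjects) repeats every row of the Section 6.0 table but gives no total. Aim 2 in Section 3.0 describes the pilot with 5 oncologists and 20 patients.

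**The concern.** A total printed beneath a list of maxima should be the sum of that list unless the document explains otherwise. Here the patient subtotal is that sum and the clinician subtotal is not, with no explanation for the difference. Section 6.0 is also the only place that states how many people the whole project may enrol. A team that stayed within every cohort maximum could exceed the stated total by 35 people. A reader also cannot tell whether the pilot is meant to involve up to 40 clinicians, as its rows say, or about 5, as the total implies. Section 5.3 has a smaller inconsistency of the same kind within one sentence.

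**Working it through.** **Inputs.** The row maxima come from Section 6.0, and Section 25.0 gives the same rows.

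| Activity | Patients | Clinicians |
|---|---|---|
| 1 | 20 + 20 | 20 + 20 |
| 3 | 12 + 12 | 10 |
| 4 | 20 | 20 + 20 |
| 5 | 30 | none |

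Activity 2 enrols nobody.

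**Step 1: the plan's own figures.** The stated subtotals give 114 + 55 = 169, so the total agrees with them. Any error must therefore lie in a subtotal.

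**Step 2: patients.** 20 + 20 + 12 + 12 + 20 + 30 = 114, as stated. The gift-card counts in Section 28.0 give the same number: 40 + 12 + 12 + 20 + 30 = 114. Patients are thus counted as a plain sum of the cohort maxima.

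**Step 3: clinicians.** 20 + 20 + 10 + 20 + 20 = 90, against 55 stated. The shortfall is 90 − 55 = 35.

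**Step 4: total.** 114 + 90 = 204, against 169 stated. The shortfall is 204 − 169 = 35, which is 35/204 = 17.2% of the correct sum.

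**Step 5: can 55 be recovered from the rows?** Every clinician row is a multiple of 10, so no selection of rows can add to 55. With Activities 1 and 3 left as they are (20 + 20 + 10 = 50), Activity 4 would have to contribute 55 − 50 = 5 clinicians, where its rows give 20 + 20 = 40. Five is the number of oncologists in Aim 2, since 20 + 20 + 10 + 5 = 55 and 114 + 55 = 169. This suggests a total that was not updated when the Activity 4 clinician cohorts were set, but the documents do not say so.

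**Step 6: Activity 3.** 12 + 12 + 10 = 34, against 32 stated in Section 5.3, a difference of 2. Section 6.0 uses the rows 12, 12 and 10, so this slip does not carry into the study-wide total.

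**The case against.** Three points can be made on the other side.

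1. **Overlap between activities.** The clinicians all come from one institution's cancer clinics, and nothing bars a clinician from joining more than one activity. The number of distinct clinicians could be below 90. That is true, and 90 is best read as a count of cohort places. But no rule for counting people once is stated, the patient subtotal beside it is a plain sum, and nothing leads from overlap to 55 in particular. The match in Section 28.0 supports the patient count only, because that section lists no clinician payments.

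2. **The total may be right and the rows wrong.** The total fits the 5 oncologists in Aim 2. This cannot be excluded. However, Sections 5.4, 6.0 and 25.0 all give 20 nurse navigators and 20 physicians and mid-level providers, so the rows are much better supported. What stands is that the choice belongs to the sponsor and that Aim 2 should be brought into line with it.

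3. **The 32 may be an overall cap.** All the Activity 3 figures are ceilings, and a joint ceiling below their sum is possible. Section 5.3 expects only 5 to 6 patients in Cohort A. This is the weaker of the two findings. Still, no such cap is explained, and Sections 6.0 and 25.0 list 12, 12 and 10 without one.

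It is also fair to say that the full excess of 35 would arise only if every cohort filled. The Activity 1 clinician cohorts may stop earlier, at thematic saturation.

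**Conclusion.** The concern holds. On the plan's own rows the maximum accrual is 204 (114 patients and 90 clinicians). The stated 169 is 35 too low, entirely in clinicians. Activity 3 is understated by 2 in Section 5.3. The conclusion assumes that each row is a maximum to be added, as the plan itself does for patients, and that no unstated rule for counting a clinician once applies.

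The consequence is limited to a wrong stated maximum, so the point is minor. Nothing in the document makes 169 a stopping limit, and no sample-size calculation or analysis uses it. Patient accrual, the pilot size of up to 20 patients, and the feasibility and acceptability outcomes in Section 10.0 do not depend on it.

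**What to change.** **Section 6.0.** Restate the total accrual as 204 participants: 114 patients and 90 clinicians. If fewer pilot clinicians are intended, instead change the Activity 4 clinician rows in Sections 5.4, 6.0 and 25.0 so that they agree with the stated total. For 55 and 169 to stand, those rows would have to total 5. If clinicians are to be counted once across activities, state that rule and derive the subtotal from it.

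**Section 5.3.** Change 32 to 34. If a joint cap of 32 is really meant, say so there and in Sections 6.0 and 25.0.

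**Section 3.0, Aim 2.** It would help to align the 5 oncologists with whichever number of pilot clinicians is chosen.

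**Cost.** The first option needs only a few corrected figures in the next amendment. Changing the Activity 4 rows touches three sections. Neither option adds recruitment beyond the cohort maxima already planned.

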7.0 Study-Wide Recruitment Methods*

Each activity utilizes slightly different recruitment methods. See section 5.0 for details.

8.0 Multi-Site Research*

Not applicable – this is NOT a multi-site research project.

9.0 Study Timelines*

The duration of an individual subject's participation in the study and the duration anticipated to enroll all study subjects varies by activity. See section 5.0 for details.

The first 5-6 quarters of the project will be dedicated to developing STAMP and conducting UAT. We anticipate enrolling 4-5 patients per week on our pilot, and should thus complete the study within 3-4 months. The study timeline may change due to unforeseen circumstances.

The estimated date for the investigators to complete this study (complete primary analyses) is August 31, 2021.

10.0 Study Endpoints*

Analysis of activity 1 (Focus groups and interviews):

Because interviews produce qualitative results, statistical analyses will not be employed as part of this study. The study team will review qualitative feedback from both patients and clinicians across the four cohorts and find common themes. The study team will use the common themes to guide development of the application.

Analysis of activities 2 (application build) – Not applicable.

Analysis of activity 3 (user acceptability testing):

Patients that take part in UAT will complete a validated usability survey⁵⁷ and respond to open-ended questions about the app.^{58, 59} Verbal/non-verbal data will be transcribed and qualitatively analyzed to identify common themes related to usability problems and comprehension. Detailed qualitative analysis is not appropriate for this aim. Rather, the goal is to identify and address any problems with the tools. After responsive revisions, additional patients will participate in additional testing. UAT will occur until no new themes emerge, and the average usability score exceeds 4 (out of 5 on a 5-point Likert scale).

With identical methodology, providers that take part in UAT will “think aloud” using the clinician interfaces of STAMP, with iterative revisions and repeat testing as needed. The think-aloud method is the most common form of UAT for health technology, and has been shown to identify >70% of usability problems within the first few interviews.^{60, 61}

Analysis of activity 4 (pilot testing): The primary outcomes for the pilot study relate to feasibility and acceptability.

- Feasibility: Descriptive statistics will characterize the proportion of eligible days on study that they complete a STAMP symptom survey, and the number of times patients log into the application. Other metrics of feasibility will include the study participation rate (proportion of eligible patients approached who consent to the study), completion rates of each study assessment, and the proportion of patients who consent and enroll on study who complete the study.
- Acceptability: summary statistics will characterize acceptability ratings (e.g. mean and standard deviation), using #7 from our modified acceptability scale as our primary acceptability measure (“how would you rate your overall satisfaction with My Pain Pal App?”, with response options ranging from 1-5). Summary statistics will also assess acceptability on domains of ease of use, understandability, enjoyability, time required for use, learning, helpfulness, and likely to recommend to another patient.
- Usability: summary statistics will characterize usability from the system usability scale
- Exploratory outcomes: we will examine the number of symptom alerts generated by STAMP, the proportion of alerts that result in clinical action (e.g. phone calls or clinic visits), and medication changes.

Exploratory analyses will evaluate patient's symptom trajectories using a marginal model with GEEs, and mixed-effects models with patient as the random and time as the fixed effect.⁶⁴

Analysis of activity 5 (qualitative patient interviews): Because interviews produce qualitative results, statistical analyses will not be employed as part of this study. Qualitative thematic analysis will use a grounded theoretical approach in which two or more investigators will code transcripts and assign labels using an open coding approach. Investigators will name concepts and revise coding until consensus is reached. Analyses will be conducted using NVIVO analytic software, which the study PI will receive training in as part of this project.

ENDPOINT: The study team will use the qualitative results to help develop a new pain mobile health app for cancer patients.

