Cohort A – Patient Lab UAT: After providing consent, participants will schedule a time to take part in the study interview. Next, the interview will be conducted with the internal study team in a private room in DFCI, or remotely via a HIPPA-compliant secure video-chat platform (i.e. Zoom). Participants will be provided a study phone with the application already downloaded onto it, or they will be provided a link to temporarily download the STAMP application onto their own phone (depending upon patient preference). Participants will be recorded while asked to “think aloud” for 30-60 minutes as they use STAMP. Think-aloud is the most common health technology UAT method, identifying >70% of usability problems within the first few interviews.^{104,105} Verbal/non-verbal data will be transcribed and analyzed qualitatively to identify themes related to usability concerns and in response to open-ended questions about the app.

Participants will then be guided through a semi-structured interview about the usability and acceptability of the application and subsequently complete a validated usability survey (the e-acceptability scale) (Appendix ZA). Medical record abstraction will then be completed for each enrolled participant (Appendix XA).

Detailed qualitative analysis is not appropriate for this aim. Rather, the goal is to identify and address any problems with the proposed application. Iterative revisions will occur in response to these themes, after which we will enroll additional patients. UAT will continue until no new themes emerge and usability scores are ≥ 3 out of 5. We anticipate conducting UAT with 5-6 patient participants, and no more than 12 participants. Each participant will receive a \$25 gift card upon completion of the study activity.

Cohort B – Patient Field UAT: After completion of testing with Cohort A and modifying the application in response, the study team will conduct field testing with up to 12 participants. Participants in Cohort B will be asked to use the STAMP app at home for up to a week (on their own mobile device), which involves completing daily symptom assessments within the app and reviewing educational resources within the app as desired.

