A structured medical record abstraction will be completed for each enrolled participant at the end of the study period to assess any clinical interactions (i.e. phone calls, clinic visits), healthcare utilization (i.e. ER visit or hospitalization for pain), or changes in pain/symptom management over the one-week study period and the week after (Appendix XB).

Cohort C: Clinician Lab UAT: Concurrent to Cohort A testing, we will conduct UAT of the web-based clinician portal of the application with relevant clinicians. With similar methodology to Lab UAT for Cohort A, up to 10 clinicians will "think aloud" while reviewing the clinician interfaces of STAMP (pre-populated with a set of test cases, not real patient data). Clinicians will be directly observed by the study team using a secure video-based screen-sharing platform (i.e. Zoom), or in person. Sessions will be recorded to assist with note taking. Following "think aloud" testing, clinicians will undergo a brief semi-structured debriefing interview and complete a validated usability survey (modified acceptability e-scale) (Appendix ZC). Clinicians will also complete a demographics survey (Appendix Y).

Findings will inform iterative revisions with repeat testing as needed. If common barriers are observed, the tool will be modified and repeat field UAT will be conducted until STAMP is found to be usable to most patients and providers.

Monitor subjects for safety or minimize risks:

The risks to participants in cohorts A, B, and C are minimal. The primary risk is loss of confidentiality/privacy. To monitor the risk of loss of confidentiality/privacy, the study team will ensure that the STAMP app is HIPPA compliant and meet the privacy and security standards set by DF/HCC. In addition, all collected study data will be maintained in a secure location and personal identifiers will be removed. As described above, UAT interviews will be recorded for the purpose of note-taking only, and will be destroyed as soon analysis concludes.

First, it is important to note that patient symptoms are imported into the clinician portal and severe symptoms are highlighted in red. This portal will be monitored once or twice per day by the study nurse. Therefore, patient symptoms will be reviewed more often by the team than with standard care practice and we anticipate they will receive earlier outreach for potentially worrisome symptoms.

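### User acceptability testing of the same Cohort A patients ends on two different score thresholds, and two stated participant totals do not equal the sum of their own cohort limits

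*Combined protocol and SAP*

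**What the plan says.** **Stopping rule.** In Section 5.3, under Cohort A (patient laboratory UAT), the rule reads "UAT will continue until no new themes emerge and usability scores are" at least "3 out of 5. We anticipate conducting UAT with 5-6 patient participants, and no more than 12 participants". The text does not say whether the scores are averaged over patients or each must reach the threshold.

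Section 10.0, in the analysis of Activity 3, opens with "Patients that take part in UAT will complete a validated usability survey", so it covers patients in both Cohort A and Cohort B. It then gives its own rule: "UAT will occur until no new themes emerge, and the average usability score exceeds 4 (out of 5 on a 5-point Likert scale".

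**Totals.** The Section 6.0 table lists these maxima:

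- Activity 1: 20 + 20 patients and 20 + 20 clinicians.
- Activity 3: 12 + 12 patients and 10 clinicians.
- Activity 4: 20 patients, 20 nurse navigators, and 20 physicians and mid-level providers.
- Activity 5: 30 patients.

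The total row gives 169, made up of 114 patients and 55 clinicians. Section 25.0 repeats the activity rows without a total. Section 5.4 gives the same Activity 4 limits.

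The subject count in Section 5.3 gives a maximum of 32 for Activity 3, and in the same sentence gives cohort limits of 12, 12 and 10.

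**The concern.** Both stopping rules share the condition on new themes, and both are written as the rule that ends patient testing. They differ in the cutoff (3 or 4), the inequality (at least, or above) and the statistic (unspecified, or an average). On one set of Cohort A scores, the team could stop under one section and be told to revise and enrol more patients under the other. A later report that UAT met its criterion would leave open which criterion was meant.

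The totals matter for oversight. In the text supplied, Section 6.0 is the only place with a study-wide maximum, and its total row does not agree with the cohort limits above it.

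**Working it through.** **1. The stopping rules compared.** Let m be the mean score of the patients tested and s_min the lowest score.

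- Section 10.0 stops if m > 4.
- Section 5.3, read as an average, stops if m ≥ 3.
- Section 5.3, read as every score, stops if s_min ≥ 3.

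*If Section 5.3 means an average:* both rules continue for m < 3 and both stop for m > 4. They disagree for 3 ≤ m ≤ 4. Any m above 4 is also at least 3, so meeting the Section 10.0 rule meets both.

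*If Section 5.3 means every score:* the disagreement can run in either direction. These illustrations use six patients, since Section 5.3 expects 5 or 6 in Cohort A:

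| Scores | m | s_min | 5.3, average | 5.3, every score | 10.0 |
|---|---|---|---|---|---|
| 3,3,3,4,4,4 | 21/6 = 3.50 | 3 | stop | stop | continue |
| 4,4,4,4,4,4 | 24/6 = 4.00 | 4 | stop | stop | continue |
| 5,5,5,5,5,2 | 27/6 = 4.50 | 2 | stop | continue | stop |
| 5,5,4,4,4,4 | 26/6 = 4.33 | 4 | stop | stop | stop |

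The third row shows that neither rule contains the other on the every-score reading. The fourth shows that one set of scores can satisfy both rules on either reading.

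**2. The study-wide total.** The stated total agrees with its own subtotals: 114 + 55 = 169. From the rows:

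- Patients: 20 + 20 + 12 + 12 + 20 + 30 = 114, as stated.
- Clinicians: 20 + 20 + 10 + 20 + 20 = 90, against 55 stated.
- Sum: 114 + 90 = 204. By activity, 80 + 34 + 60 + 30 = 204.
- Gap: 204 − 169 = 35, which equals 90 − 55. It lies wholly in the clinician subtotal, and 35/204 = 17%.

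The Activity 1 and Activity 3 clinician rows take 20 + 20 + 10 = 50 of the 55. That leaves 5 for Activity 4, whose row allows 40.

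Full clinician cohorts alone would exceed the clinician subtotal by 35. They would not by themselves exceed 169: with 90 clinicians, that figure is passed only above 169 − 90 = 79 patients, and by 35 only at all 114.

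**3. Activity 3.** 12 + 12 + 10 = 34, against 32 stated, a gap of 2.

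**The case against.** **The thresholds can both be met.** This is correct, and a reader who called them incompatible would go too far. They are two different thresholds, and on the averaged reading a cautious team could follow the stricter one and satisfy both. The plan does not say to do so, and on the every-score reading there is no uniformly stricter rule.

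**The rules may be staged.** The Section 5.3 rule sits in the Cohort A text and could be a lower bar before field testing, with Section 10.0 as the final bar. No section describes such stages, and the near-identical wording of the two rules weighs against it.

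**There may be a third rule, or a missing clinician threshold.** A reader might infer a third stopping rule from Section 5.3, where, after changes prompted by shared problems, "repeat field UAT will be conducted until STAMP is found to be usable to most patients and providers". That sentence is conditional, concerns repeat field testing and gives no score, so it does not compete with the two thresholds. A reader might also fault the plan for giving clinicians no clear threshold, since it says "With identical methodology, providers that take part in UAT will" in Section 10.0 and "With similar methodology to Lab UAT for Cohort A, up to 10 clinicians will" in Section 5.3. Section 10.0 has provider testing repeated as needed, and the plan does not have to set a clinician score.

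**The totals may be deliberate.** The 55 could count each clinician once across activities, and 32 could be a joint cap below the sum of the cohort limits. Neither is stated. The patient subtotal is a plain sum of the same rows, which suggests that the total row is meant as a sum. Sections 6.0 and 25.0 repeat 12, 12 and 10 with no joint cap. Aim 2 in Section 3.0 names 5 oncologists, which would explain the 5 left over for Activity 4, but that source is an inference.

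**Little depends on it.** This stands. Cohort A is capped at 12 patients under either threshold, and UAT is there to find and fix problems.

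**Conclusion.** The point holds and is minor. Cohort A testing has two different score thresholds with no statement of which governs. The size of the disagreement depends on what Section 5.3 means. If it means an average, the rules split on averages from 3 to 4 inclusive. If it means every score, they can conflict in both directions. The Section 6.0 total is 35 below its rows, all in clinicians, and the Activity 3 figure is 2 below its cohort limits. These two findings assume that the totals are meant as sums of the listed maxima.

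A reader might infer that the pilot could start on an app that failed its test, or that the pilot's results are compromised. The documents do not support either. No section makes the UAT score a formal condition for starting the pilot, and the patient maximum of 114, the pilot size of 20 and the pilot's descriptive analyses are unaffected.

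**What to change.** - **Threshold.** State one UAT score threshold, say whether it is an average or applies to every score, name the patient cohorts it covers, and use it identically in Sections 5.3 and 10.0. If UAT is complete, state which rule was applied and the score reached.
- **Study-wide total.** Restate the Section 6.0 total as 204 (114 patients, 90 clinicians) if the Activity 4 limits in Sections 5.4, 6.0 and 25.0 stand, as their agreement suggests. Otherwise lower the clinician cohort limits.
- **Activity 3.** Restate the Section 5.3 figure as 34, or say that 32 is a joint cap.

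The cost is small. The threshold and the Activity 3 figure are wording corrections. Raising the stated maximum from 169 to 204 may need an IRB amendment, a route this protocol already uses. If UAT is still open and the stricter threshold is chosen, a few more sessions may be needed within the existing cohort limits.
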